## PROTOCOL UPDATE HISTORY

VERSION	DATE	REASON FOR UPDATE
1.0	26/12/2018	Initial version
2.0	02/11/2019	Request for information or modifications
3.0	02/20/2021	Amendment request for study extension

## SUMMARY

### ABBREVIATIONS LIST

ARCClinical research associate

StrokeCerebrovascular accident

ANSMNational Agency for the Safety of Medicines and Health Products

CPPCommittee for the Protection of Persons

EMAEuropean Medicines Agency

MACEMajor Adverse Cardiac Events

TECClinical research technician

## SUMMARY OF RESEARCH

PROMOTER	Hospital Group of La Rochelle Ré Aunis [name] 17019 La Rochelle
PERSON LEADING THE RESEARCH	[name] [name] Cardiology service Hospital Group La Rochelle-Ré-Aunis
TITLE	SAFETY EVALUATION OF ANGIOPLASTY INTERVENTIONS (SCRAP)
RATIONALE/CONTEXT	Ischemic heart disease, or coronary heart disease, covers a set of pathologies due to insufficient oxygen supply to the myocardium due to the development of atherosclerosis in one or more coronary arteries. The use of active stents for the treatment of coronary stenosis is currently the standard treatment in almost all types of coronary lesions. In the percutaneous transluminal treatment of coronary lesions, angioplasty with balloons and bare stents has not shown satisfactory results in the past. The drug-eluting, so-called active balloon, could represent a new therapeutic option for the treatment of de novo lesions.
GOALS	To assess the safety of angioplasties performed in patients operated on at La Rochelle Hospital, the rate of major adverse cardiac events (MACE) will be determined and analyzed in the light of data from the literature.
RESEARCH SCHEME	non-interventional, prospective, monocentric research.
INCLUSION CRITERIA	
 
• Patient treated for angioplasty,
 
• Person affiliated or beneficiary of a social security scheme,
 
• Informed about the study.
 

NON-INCLUSION CRITERIA	
 
• language barrier,
 
• Minor,
 
• Pregnant woman,
 
• Person under guardianship or curatorship,
 
• person deprived of liberty,
 
• Refusal to participate.
 

EVALUATION CRITERIA	The primary endpoint is a composite endpoint of major adverse cardiac events defined as death, nonfatal myocardial infarction (MI), nonfatal stroke (stroke), and target lesion revascularization (TLR) within 12 monthsthen at 36 monthsfollowing the intervention.
STUDY SIZE	The objective is to include more than 80% of patients over a period of 12 months, ie 1000 patients.
SEARCH DURATION	
 
• Duration of the inclusion period: 12 months
 
• Duration of follow-up per participant:36months (telephone contact at 12 monthsthen at 36 monthsfor MACE collection)
 
• Total search time:48 month
 

STATISTICAL ANALYSIS OF DATA	The parameters collected are presented in tables containing descriptive and comparative statistics (total population; small vessel/large vessel subpopulations; stent[s]/stent[s] and active balloon[s]/active balloons subpopulations assets]). The MACE rate corresponds to the ratio of the number of patients who had one or more MACE to the total number of patients for whom the follow-up was carried out at 12 monthsthen to36month. The study of risk factors for MACE is carried out by bivariate analysis.
EXPECTED BENEFITS	The results of this study will make it possible to validate or not the algorithm of care applied to the hospital of La Rochelle. The results will be communicated to the Coronary Atheroma and Interventional Cardiology Group (GACI).

## **SCIENTIFIC RATIONALE AND GENERAL DESCRIPTION**

### **CURRENT STATE OF KNOWLEDGE**

Ischemic heart disease, or coronary heart disease, covers a set of pathologies due to insufficient oxygen supply to the myocardium due to the development of atherosclerosis in one or more coronary artery(ies). The use of active stents for the treatment of coronary stenosis is currently the standard treatment in almost all types of coronary lesions. In the percutaneous transluminal treatment of coronary artery lesions, balloon angioplasty with conventional balloons and drug-free eluting stents have not shown satisfactory results.(1)(2). Although some studies have shown balloon angioplasty and bare stent placement to be equally effective against restenosis(1)(2), a meta-analysis of 11 trials finds a rate of 25.8% for balloon angioplasty and 34.2% for bare-metal stents(3).

Thrombosis and in-stent restenosis, despite a decreasing incidence since the advent of first and then second generation active stents, remain frequent complications of angioplasty at around 5 to 15% depending on the series. (4.5). Indeed, the implantation of stents in the arterial wall leads to an inflammatory reaction around the mesh as well as the persistence of fibrinous deposits at the origin of a neointimal proliferation that is more thrombogenic than the native endothelium. (6). To this is added a phenomenon of neoatherosclerosis which appears later than on bare stents, most often 3 years from the date of implantation. On the other hand, very late stent thromboses, defined by the Academic Research Consortium as occurring more than one year after stent implantation, in fact require prolonged observation in order to take them into account.

The drug-eluting balloon, also called active balloon, or DCB (Drug Coated Balloon), was initially developed for the treatment of in-stent restenosis (4), and is currently considered the standard treatment for this pathology instead of in-stent active stenting. Since then, the active balloon has gradually been studied for the treatment of de novo lesions (5), particularly those of small vessels. The multicenter randomized BASKET-SMALL study on small de novo lesions (less than or equal to 2.5 mm in diameter) showed the non-inferiority of drug-eluting balloons compared to the active stent with regard to MACE up to 12 months, with similar event rates for both treatment groups(7).

Recently, pilot studies have demonstrated the feasibility of using drug-eluting balloons for the treatment of bifurcations(8), chronic occlusions(9), as well as calcified lesions after Rotablator(10). These studies have thus shown very promising and consistent results when the active balloon was used as an alternative therapy. The German consensus group has therefore recently developed recommendations for the treatment of small vessel disease using the drug-eluting balloon(11).The BASKET SMALL 2 study is the first study to have compared the effectiveness of the active balloon versus an active stent in the treatment of de novo lesions of small vessels, with a fairly long follow-up period of 3 years and in a sufficiently large workforce. (12).Other studies have been able to demonstrate good results at 6 months in terms of efficacy and safety of the active balloon on the treatment of de novo lesions, regardless of the caliber of the vessel treated. (13). However, data are lacking in the literature concerning the treatment

of de novo lesions by active balloon, with a sufficiently long follow-up period to take into account neo-atheromatosis and very late stent thrombosis, in a large sample.

The use of drug-eluting balloons in La Rochelle has gradually evolved from the in-stent indication, to de novo lesions of small vessels ( $\leq 2.5$  mm), then to de novo lesions of large vessels. In addition to the treatment of long lesions on small caliber vessels, good immediate angiographic results are also obtained for the treatment of bifurcations (all types of Medina), for calcified lesions pretreated with Rotablator, as well as certain chronic occlusions.

### **RESEARCH ASSUMPTIONS**

To assess the safety of angioplasties performed in patients operated on at La Rochelle Hospital, the rate of major adverse cardiac events (MACE) will be determined and analyzed in the light of data from the literature.

### **JUSTIFICATION OF METHODOLOGICAL CHOICES**

The collection of data on MACE will be carried out by telephone follow-up at 12 monthsthen at 36 months. Major adverse cardiac events are defined as death, myocardial infarction, and ischemia-induced target lesion revascularization during the follow-up period.

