## GOALS

### 1.1. PRIMARY OBJECTIVE

To assess the safety of angioplasties performed in patients operated on at La Rochelle Hospital, these will be referred to as 12 monthsthen at 36 monthsafter the operation to find out if any major adverse cardiac events (MACE) have occurred since their operation. The MACE rate will thus be determined.

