## EVALUATION CRITERIA

The primary endpoint is a composite endpoint of major adverse cardiac events defined as death, nonfatal myocardial infarction (MI), nonfatal stroke (stroke), and target lesion revascularization (TLR) within 12 months then 36 months following the intervention.

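### Two current definitions of MACE conflict: one omits stroke, which the primary endpoint includes, and they disagree on whether target lesion revascularization must be ischemia-driven

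*Combined protocol and SAP*

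**What the plan says.** Under Justification of Methodological Choices, directly after the sentence on telephone follow-up at 12 and 36 months, the protocol gives a three-component list: "Major adverse cardiac events are defined as death, myocardial infarction, and ischemia-induced target lesion revascularization during the follow-up period".

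Evaluation Criteria, the section that names the primary endpoint, gives four components: "death, nonfatal myocardial infarction (MI), nonfatal stroke (stroke), and target lesion revascularization (TLR) within 12 months then 36 months following the intervention". The evaluation-criteria row of the Summary of Research lists the same four.

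The only rate defined is the MACE rate, "the ratio of the number of patients who had one or more MACE to the total number of patients" with follow-up carried out. Section 1.1 (Primary Objective) has patients called "to find out if any major adverse cardiac events (MACE) have occurred since their operation". Research Assumptions says that "the rate of major adverse cardiac events (MACE) will be determined and analyzed in the light of data from the literature".

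The research timeline, the monitoring table, Follow-up Visits, section 1.3 (Statistical Methods Used) and Data Management all use the term MACE without listing components. The abbreviations list only spells the term out.

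**The concern.** The study has one objective, one event outcome and one defined rate, and all three depend on what counts as MACE. The same outcome is also the dependent variable of the risk-factor odds ratios. Two current sections answer the question differently, and no section says which takes precedence.

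The three-component list stands next to the sentence on telephone collection, where someone preparing the calls might well look. The documents contain no call script and no field list, so they do not show whether stroke is asked about. Follow-up Visits has the cardiologist contacted for details only when a MACE has occurred. Under the three-component list, a patient whose only event was a stroke would not be counted and would not trigger that contact.

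Omitting stroke can only lower the rate, which is the reassuring direction in a safety study. A three-component rate also cannot be compared like for like with four-component rates from the literature. A larger sample would not correct either problem.

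**Working it through.** **Side-by-side comparison**

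| Component | Justification of Methodological Choices | Evaluation Criteria and Summary of Research | Consequence |
|---|---|---|---|
| Death | included | included | none |
| Myocardial infarction | any | nonfatal | none: a fatal infarction already counts as death |
| Stroke | absent | nonfatal stroke included | conflict |
| Target lesion revascularization | ischemia-induced only | no qualifier | unresolved: all, or ischemia-driven only |

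The narrower definition is current text. It is not part of an amendment log and does not describe a cited study.

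**Does it affect the planned size?** No. Study Size Calculation takes 80% of the 1,252 patients treated in 2017: 0.80 × 1,252 = 1,001.6, which reproduces the stated 1,000. This is a recruitment target with no expected MACE rate behind it, so only the estimate is at risk.

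**Size of the shortfall if the three-component list was used.** Let P be the four-component rate and s the share of patients whose only event is a stroke. The counted rate is then P − s. If all revascularizations are meant, patients whose only event is a revascularization that was not ischemia-driven add to the shortfall. That part is not quantified here. The documents give neither P nor s, so the values below are assumptions.

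The half-width of the 95% interval at P is 1.96 × √(P(1 − P)/n). For P = 10% and n = 1,000 this is 1.96 × √(0.10 × 0.90/1,000) = 1.86 points.

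| P | n = 1,000 | n = 800 (assumed followed) |
|---|---|---|
| 5% | 1.35 points | 1.51 points |
| 10% | 1.86 points | 2.08 points |
| 20% | 2.48 points | 2.77 points |

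The shortfall exceeds the half-width once s passes these values. Take s between 0.5% and 1.5% at 12 months, that is 5 to 15 patients per 1,000. With n = 1,000 the shortfall stays below the half-width at rates of 10% and 20%, but its upper end exceeds the half-width at 5% (1.5 against 1.35 points).

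**A bias below the half-width still matters.** The table gives the exact binomial probability that the usual (Wald) 95% interval, computed from the under-counted events, contains P, for n = 1,000:

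| P | s = 0 | s = 0.5% | s = 1.5% |
|---|---|---|---|
| 5% | 94.2% | 83.8% | 26.8% |
| 10% | 95.3% | 90.9% | 60.6% |
| 20% | 94.7% | 92.3% | 75.4% |

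**The case against.** The strongest reply is that the primary endpoint is not undefined. The section that names it and the summary agree on four components. The conflicting sentence sits in a justification section and never uses the words primary endpoint. The abbreviations list has an entry for stroke ("StrokeCerebrovascular accident"), which also favours the four-component list. No text shows that staff followed the narrower list, the sample size is unaffected, and no threshold is set that the rate could pass or fail. On this view the defect is one unaligned sentence.

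Much of this stands. A reader would probably treat the four-component list as governing for stroke, and if staff did so no strokes are lost. But that settles the analysis, not what was collected, and the narrower list is the one beside the collection sentence. Nor does it settle revascularization, because an unqualified term does not show whether the qualifier was intended.

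Four smaller objections also have weight:

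- The rates and stroke-only shares are assumed, so the coverage figures illustrate the effect and do not measure it.
- The half-widths are computed at P, whereas the reported interval would be computed at P − s and be narrower. For P = 5% and s = 1.5%, 1.96 × √(0.035 × 0.965/1,000) = 1.14 points, not 1.35. The comparison above is therefore slightly lenient to the plan.
- The downward direction holds for the three-component list set against the four-component wording. If the sponsor means ischemia-driven revascularization only and staff counted every one, the rate would be too high.
- The cardiologist's detailed record may already allow ischemia status to be recovered for revascularizations that were reported.

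**Conclusion.** The concern holds. The sole primary endpoint has two incompatible definitions in current text. The stroke conflict is certain, and the revascularization term is ambiguous under either reading. Because this is a contradiction in the only outcome the study reports, it must be corrected.

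The practical effect depends on which list the callers used, and the documents do not show this. If they used four components, no strokes are lost and what remains is the unaligned sentence and the open revascularization term. If they used three, the rate is biased downward by the stroke-only share, by an amount the documents do not allow anyone to calculate. On the assumed share of 0.5% to 1.5% the loss would be 5 to 15 patients per 1,000. That is enough to damage interval coverage, most severely when the true MACE rate is low. The effect of the revascularization ambiguity is unquantified and could go in either direction.

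**What to change.** 1. In Justification of Methodological Choices, replace the definition with the four-component list in Evaluation Criteria.
2. Have the sponsor state whether every target lesion revascularization counts or only those that are ischemia-driven, and use the same wording there, in Evaluation Criteria and in the Summary of Research. The documents do not show which is meant.
3. In the monitoring table, have the MACE row refer to the Evaluation Criteria list.
4. In the follow-up table described under Data Management, record stroke (yes/no) and, for each revascularization, whether it was ischemia-driven, if these fields are not already there. Either version of the endpoint can then be computed.
5. If any 12-month calls did not ask about stroke, ask at month 36 about the whole period since the intervention. Also check the records named under Source Data for those patients, including any who died or cannot be reached at month 36. For those who died by then, the check bears only on the 12-month rate, since death already counts at 36 months. Those records are the hospital file and city cardiologists' reports, so a stroke managed elsewhere may be missed. The report should say so.

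The cost is one aligned sentence, one definition, one cross-reference and at most two data fields, with no extra patients or calls. Only if step 5 applies is a records check added, and a 12-month rate computed without stroke would then have to be recomputed.

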### **EXPECTED BENEFITS**

The results of this study will make it possible to validate or not the algorithm of care applied to the hospital of La Rochelle.

The results will be communicated to the Coronary Atheroma and Interventional Cardiology Group (GACI).

[figure not shown]

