## RESEARCH DESIGN

This is non-interventional, cross-sectional, prospective, monocentric research.

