#### **1.3. STATISTICAL METHODS USED**

The parameters collected are presented in tables with descriptive statistics for the total population and for the sub-populations defined by the size of the vessels (small vessels / large vessels) or the procedure used (active stent[s] / stent [s] and balloon[s] active[s] / balloon[s] active[s]), according to the following modalities:

- For quantitative variables: the mean and the standard deviation or the median, the minimum and the maximum
- For qualitative variables: the number, percentages and 95% confidence interval, for each of the modalities of the variable (excluding missing data in the denominator).

The MACE rate will correspond to the ratio of the number of patients having had one or more MACE to the total number of patients for whom the follow-up was carried out at 12 months.then at 36 months.

To compare the sub-populations, the analyzes test the null hypothesis of equality of means for the quantitative variables and of homogeneity of the populations for the qualitative variables:

- For the quantitative variables, after checking the equality of the variances and the normal distribution of the values, the Student test is used. In case of inequality of variances or non-Gaussian distribution, a non-parametric Mann-Whitney/Wilcoxon test is used.
- For qualitative variables, a chi-square test is carried out or a Fisher test in the case of small numbers.

The study of risk factors for MACE is carried out by bivariate analysis. Odds ratios and 95% confidence intervals are calculated.

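### The protocol promises a yes-or-no verdict on the care algorithm, but none of its planned analyses sets the algorithm against an alternative strategy or a pre-specified reference rate

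*Combined protocol and SAP*

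**What the plan says.** In the combined protocol and SAP, the Expected Benefits section states that the results "will make it possible to validate or not the algorithm of care applied to the hospital of La Rochelle". The Expected Benefits row of the Summary of Research repeats this: "validate or not the algorithm of care applied to the hospital of La Rochelle". Both places add that the results go to the coronary atheroma and interventional cardiology group.

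The rest of the document describes estimation:

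- **Objective** (1.1 Primary Objective): "The MACE rate will thus be determined".
- **Design** (Research Design): "This is non-interventional, cross-sectional, prospective, monocentric research". No concurrent or historical control is described.
- **External comparison** (Research Assumptions, repeated in the Goals row of the Summary): the MACE rate "will be determined and analyzed in the light of data from the literature".
- **Primary analysis** (1.3 Statistical Methods Used): "The MACE rate will correspond to the ratio of the number of patients having had one or more MACE", divided by the patients followed up, at 12 and then 36 months.
- **Other analyses** (same section): tables and tests by vessel size and by device group (stent, stent plus balloon, balloon), and bivariate odds ratios for MACE risk factors.

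**The concern.** Validating an algorithm, or declining to, is a decision. It needs either a contrast between patients managed under the algorithm and patients managed otherwise, or at least a reference value and a rule fixed in advance, together with some means of separating the algorithm's effect from case mix. The plan appears to have none of these.

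A cohort of low-risk patients could then make a poor algorithm look validated, and a cohort of high-risk patients could make a good one look rejected. The reader of the final report would have no pre-stated criterion against which to check the conclusion.

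**Working it through.** **1. The study size.** Study Size Calculation gives 1,252 patients treated in 2017 and a target above 80%, stated as 1,000. Check: 0.80 × 1,252 = 1,001.6, so the figure reproduces to rounding (1,000 / 1,252 = 79.9%). It is a share of annual volume. No expected MACE rate, threshold, margin, alpha or power is given, so the size carries no implicit decision rule.

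**2. Precision.** The 95% half-width is 1.96 × √(p(1−p)/n). With n = 1,000 it is 1.4 points at p = 5%, 1.9 at 10% and 2.2 at 15% (assumed rates). Precision is adequate for description. What is missing is something to compare the rate with.

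**3. Each planned output against what a verdict needs.**

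- *MACE rates at 12 and 36 months.* All patients come from one centre that applies one algorithm, and there is no control. The rates describe outcomes under the algorithm and contrast it with nothing.
- *Comparisons by device group.* Procedures Studied shows that the device is chosen on instability, ventricular arrhythmia, dissection type, residual stenosis and bleeding risk. These are the algorithm's own criteria, so the groups differ by indication. Section 1.3 tests them with Student, Mann-Whitney/Wilcoxon, chi-square or Fisher tests and describes no adjustment.
- *Comparisons by vessel size.* These compare kinds of lesion, not ways of managing them.
- *Bivariate odds ratios.* These relate patient or procedure factors to MACE. Adherence to the algorithm is not named as a variable in any analysis.
- *Comparison with the literature.* No source, rate, margin or rule is stated anywhere, including the statistical section.

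**4. Is a benchmark implied by the rationale?** Current State of Knowledge gives 5 to 15% for thrombosis and in-stent restenosis, and 25.8% and 34.2% in a passage on restenosis. None of these is a MACE rate. The randomized small-vessel trial is cited for non-inferiority on MACE with similar event rates, but no rate or margin is quoted. No MACE benchmark can be read from the documents.

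**5. Illustration with assumed figures.** Take 100 MACE in 1,000 patients, so p = 0.10.

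Wilson 95% CI = [p + z²/2n ± z√(p(1−p)/n + z²/4n²)] / (1 + z²/n), with z = 1.96.

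- Centre: (0.10 + 0.00192) / 1.00384 = 0.1015
- Half-width: 1.96 × √(0.00009 + 0.00000096) / 1.00384 = 0.0186
- Interval: 8.29% to 12.02%

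The same result against assumed reference rates, using the two-sided exact binomial test:

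| Assumed reference | p-value | Reading |
|---|---|---|
| 8% | 0.023 | worse |
| 9% | 0.27 | no difference shown |
| 11% | 0.34 | no difference shown |
| 12% | 0.052 | borderline lower |
| 12.5% | 0.017 | better |

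The rate uses only patients followed up. With 800 followed (an assumed 20% loss) and the same 10%, the interval is 8.1% to 12.3%, so the picture is unchanged.

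**The case against.** The strongest defence is that the promise stands only under expected benefits. The objective is estimation, and nothing in section 1.3 would generate a verdict. On that view the fault is one aspirational sentence. This stands in part: the planned analyses are sound as description and need no change. But the sentence appears twice, it is the use of the results that the protocol declares, and no other text limits it.

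The illustration can also be called close to a tautology, and that is fair. Any estimate is worse than references below its interval and better than those above it. The distance between the two readings is essentially the width of the CI. The illustration shows only why a reference is needed before a verdict has meaning. It does not show that every result could be read both ways, which holds only for references near the observed rate.

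A reader might infer several stronger points that the documents do not support:

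- *That the study produces a single MACE rate.* It plans two time points, tested sub-population comparisons and risk-factor odds ratios. These do not rescue the verdict, but they exist.
- *That the reference would be picked once the La Rochelle rate is known.* The documents do not say when the literature will be chosen.
- *That the results will be presented to the cardiology group as a validation, or that this group is national.* The text says only that results will be communicated to it.
- *That the cited small-vessel trial is an unsuitable comparator because this cohort includes acute coronary syndrome.* The documents neither make that trial the benchmark nor say whom it excluded.

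References 7 and 12 are the same paper. That is a separate bibliographic matter.

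**Conclusion.** The point holds as a mismatch between a stated use and the design. It is wrong as written, because the protocol claims a capability that the planned analyses do not have. This conclusion rests on reading the sections side by side and needs no numerical assumption.

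The mismatch is not merely an omitted benchmark. If a literature rate were named, a difference from it could still come from case mix, since the rates are uncontrolled and no adjusted analysis is described.

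The size can only be illustrated. At an assumed 10% rate in 1,000 patients, moving the reference from 8% to 12.5% (4.5 points) turns the reading from worse to better. The rate, the references and complete follow-up are all assumptions.

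**What to change.** Four short edits:

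- In the Expected Benefits section and the matching Summary row, replace the clause on validating the algorithm with: *describe the 12- and 36-month MACE rates, with 95% CI, in patients treated under the algorithm*.
- In Research Assumptions and the Goals row of the Summary, state that the comparison with the literature is descriptive, and that no verdict on the algorithm will be drawn from the uncontrolled rates or the unadjusted device comparisons.

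The cost is wording in those places and a matching conclusion in the report. No new data or analysis is needed, since section 1.3 already provides 95% confidence intervals for qualitative variables. The downside is a less ambitious claim.

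Keeping the verdict and adding a reference rate with a decision rule is not an equivalent remedy, because it would leave the case-mix problem untouched.
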